**REVISION HISTORY:**

*Use this table to keep track of changes. Add more rows as needed.*

Revision #	Version Date	Brief Summary of Changes (i.e., the different sections)	Consent Change?
0	4/1/19		
1	6/4/19	Added compensation, pain protocol, 6 mo f/u, changed from WIRB to BRANY	Yes
2	11/20/19	Removed LGH study site	Yes

## 1.0 Study Summary

Study Title	Using Triamcinolone Acetonide to Reduce Pain after Scleral Buckle Surgery
Study Design	Simple Randomized Control Trial
Primary Objective	To assess pain reduction following scleral buckle surgery with sub-tenon irrigation of triamcinolone acetonide, as measured by 11-point Numerical Rating Scale at 24 hrs post-op
Secondary Objective(s)	
 
Pain at 1-2 week post-op visit (11 pt NRS scale)
 
Pain at 6 mo post-op phone call
 
Post-operative analgesic consumption
 
Post-operative nausea and vomiting score (0-6)
 

Study Population	Patients undergoing Scleral Buckle Surgery for rhegmatogenous retinal detachment at Vistar Eye Center
Sample Size	N = 48
Research Intervention(s)/ Investigational Agent(s)	
 
1 cc Triamcinolone sub-tenon irrigation
 
Self-report survey at 24-hrs post-operative including 11 pt pain scale, nausea and vomiting score
 
Pill Count at 24-hrs post-operative
 
Self-report survey at 1-2 week post-operative including 11 pt pain scale, analgesic consumption, nausea and vomiting score
 
Pill Count at 1-2 weeks post-operative
 
Intra-ocular pressure measurement at 24 hrs post-operative
 
Intra-ocular pressure measurement at 1-2 week post-operative
 

Study Duration for Individual Participants	90 mins for the surgery (standard medical procedure) + 30s for experimental procedure + 2 minutes for each survey Each pt. is enrolled for 2 weeks.
Acronyms and Definitions	
IOP- Intraocular Pressure  NRS- Numerical Rating Scale for Pain  EMR- Electronic Medical Record  TA- Triamcinolone Acetonide

## 2.0 Objectives

- 2.1 *The purpose of this study is to determine if sub-tenon irrigation with triamcinolone acetonide at the time of surgery for rhegmatogenous retinal detachment will reduce the pain and inflammation caused by scleral buckle surgery.*
- 2.2 *Primary Hypothesis: Sub-tenon irrigation with 1cc (40 mg) Triamcinolone Acetonide will significantly reduce post-operative pain at 24 hrs post-*

*operation in patients undergoing scleral buckle surgery for rhegmatogenous retinal detachment.*

*Secondary Hypotheses:*

*Peri-bulbar irrigation with 1cc (40 mg) Triamcinolone Acetonide will significantly reduce post-operative analgesic consumption at 24 hrs post-operation in patients undergoing scleral buckle surgery for rhegmatogenous retinal detachment*

*Peri-bulbar irrigation with 1cc (40 mg) Triamcinolone Acetonide will significantly reduce post-operative nausea and vomiting score at 24 hrs post-operation in patients undergoing scleral buckle surgery for rhegmatogenous retinal detachment*

*Peri-bulbar irrigation with 1cc (40 mg) Triamcinolone Acetonide will significantly reduce post-operative pain at 1-2 week post-operation in patients undergoing scleral buckle surgery for rhegmatogenous retinal detachment.*

*Peri-bulbar irrigation with 1cc (40 mg) Triamcinolone Acetonide will significantly reduce post-operative pain at 6 month post-operation in patients undergoing scleral buckle surgery for rhegmatogenous retinal detachment.*

*Peri-bulbar irrigation with 1cc (40 mg) Triamcinolone Acetonide will significantly reduce post-operative analgesic consumption at 1-2 week post-operation in patients undergoing scleral buckle surgery for rhegmatogenous retinal detachment*

*Peri-bulbar irrigation with 1cc (40 mg) Triamcinolone Acetonide will significantly reduce post-operative nausea and vomiting score at 1-2 week post-operation in patients undergoing scleral buckle surgery for rhegmatogenous retinal detachment*

### 3.0 Background

#### 3.1 Summarize the relevant prior research on this topic and gaps in current knowledge within the field of study.

Scleral buckle surgery is a widely used ophthalmic surgery for the correction of primary rhegmatogenous retinal detachment. Research suggests that it is of equal efficacy as pars plana vitrectomy and that most eyes retain visual acuity for 20 years after surgery. Studies also suggest that eye pain is a common and underestimated occurrence after vitreoretinal surgery for retinal detachment, with 56% of patients reporting intense pain post-operatively. Levels of post-operative nausea were also correlated to the level of pain experienced. In a study on chronic pain following scleral buckle surgery, it was shown that all patients

## Using Triamcinolone Acetonide to Reduce Pain after Scleral Buckle Surgery

experienced pain following the surgery, with a wide range of subject pain scores. 18% of these patients experienced chronic pain for >6 months following surgery. Patients who experienced chronic pain showed higher pain scores in the immediate post-operative period. Local inflammation has been shown to be associated with eye pain in the first few days after surgery. It has also been shown that reduction of swelling following scleral buckle surgery reduces pain following surgery. Triamcinolone acetonide is a corticosteroid that is used extensively in ophthalmology for many indications including uveitis, vasculitis, proliferative vitreoretinopathy, macular degeneration, and macular edema.

Triamcinolone works by inhibiting phospholipase A2 induction, and thereby downregulating inflammatory mediators including interleukins, prostaglandins and tumor necrosis factor. Corticosteroids also have been shown to have profound anti-angiogenic effects, vasoconstrictive effects, anti-permeability effects, ability to help maintain blood-retinal barrier, and facilitation of exudate reabsorption. Furthermore, triamcinolone has relatively small particles, allowing it to be injected in or around the eye, and has a duration of action of several months. Surgery in and around the eye has been shown to cause intraocular inflammation, called uveitis. Corticosteroids are currently the cornerstone of treatment for uveitis. A study of perioperative intravitreal injection of triamcinolone during pars plana vitrectomy for open globe trauma demonstrated an improvement in visual acuity, likely due to the anti-inflammatory effects of triamcinolone. Another study using triamcinolone with bupivacaine as a peribulbar injection at the conclusion of surgery for retinal detachment demonstrated a reduction in the use of hydrocodone following surgery, and demonstrated a trend of reduced pain, though it did not reach full significance. As of yet, there is no definitive management method for reducing pain and swelling following scleral buckle surgery. We will be employing a sub-tenon irrigation approach to deliver 1cc of 40 mg / mL triamcinolone directly on the sutured area to reduce pain following surgery to try to address this gap.

### 3.2 *Describe any relevant preliminary data*

The use of Triamcinolone Acetonide sub-tenon irrigation has been done as standard at Vistar for scleral buckle surgeries for the last 2 years by [name] and [name]. Observations by the two surgeons suggest that there is a great analgesic effect for patients 24 hours post-surgically when compared to patients not given TA. There have been no noted adverse effects resulting from this use.

### 3.3 *Based on the existing literature, provide the scientific or scholarly rationale for and significance of your research and how will it add to existing knowledge.*

Currently, there does not appear to be any definitive standard of care for reduction of post-operative pain and swelling following scleral buckle surgery, as demonstrated by the wide variety of techniques employed. Multiple Vistar surgeons currently use Triamcinolone Acetonide for all scleral buckle surgeries within the system, but this practice has not yet been proven in a randomized control trial. Some physicians are prescribing opioids to control pain following scleral buckle surgery; in today's environment of opioid crises, this is something we would like to avoid. The significance of this study is that if the outcome is positive, it will help to determine a definitive standard of care for reducing pain and swelling following scleral buckle surgery that will allow reduced prescription of narcotics.

## 4.0 Study Endpoints

### 4.1 *Describe the primary and secondary study endpoints*

Primary Endpoint:

- Statistically significant reduction in pain as measured by 11-point Numerical Rating Scale at 1-day post-op. We are powered to detect a reduction in 2 points on the NRS scale.

Secondary Endpoints:

- Statistically significant reduction in pain as measured by 11-point Numerical Rating Scale at 1-2 weeks post-op.
- Statistically significant reduction in pain as measured by 11-point Verbal Rating Scale at 6 months post-op.
- Significant reduction in analgesics consumed post-operatively (self-reported pill count) at 1-day post op
- Significant reduction in analgesics consumed post-operatively (self-reported pill count) at 1-2 weeks post op
- Significant reduction in Nausea and Vomiting Score at 1 day post-op.
- Significant reduction in Nausea and Vomiting Score at 1-2 weeks post-op.

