## **7.0 Study Intervention(s)/Investigational Agent(s)**

*7.1 Describe the study interventions (including behavioral interventions) and/or investigational agents (e.g., drugs or devices) to be used in this study.*

- *Drug/Device Handling:*  
Triamcinolone will be stored in the operating facility according to package instructions: at controlled room temperature, 20° to 25°C (68° to 77°F). Vial will be stored in carton to protect from light, and will be stored upright. In the operating room, the vial will be opened according to sterile procedure by a nurse and prepared for injection by the surgeon.

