## Using Triamcinolone Acetonide to Reduce Pain after Scleral Buckle Surgery

7.2 *List the name of all drugs (including any vitamins, supplements, herbs, or nicotine) to be used in the study. Indicate whether they have FDA approval, and list any limitations for their use.*

Triamcinolone Acetonide injectable suspension. FDA Approved.

Marcaine (Bupivacaine Hydrochloride .75%). FDA Approved.

7.3 *List all devices, how they will be used, their purpose in the study, and if they will be used in a manner consistent with their approved uses. If they will be used in ways that are not yet FDA approved, indicate whether they need an IDE or a determination that they are exempt from the IDE Determination. If a determination of significant risk or non-significant risk is needed for any of the devices, include the researcher's recommendation for each of those devices.*

N/A

7.4 *If the drug is investigational (has an IND) or the device has an IDE or a claim of abbreviated IDE (non-significant risk device), include the following information:*

N/A

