## 8.0 Procedures Involved

8.1 *Describe and explain the study design.*

Randomized Control Trial. Subjects will be patients at Vistar Eye Center who are undergoing scleral buckle surgery for rhegmatogenous retinal detachment. Patients of this indication will be consented and enrolled in the trial as detailed in section 24, and randomized (by coin-flip) into one of two arms, the control or the experimental. Patients in both arms of the study will be screened for IOP via handheld digital tonometry (tonopen) and will undergo standard scleral buckle procedures, including irrigation with 1 ml .75% Marcaine for local anesthesia (as is standard for all surgeries). At time of surgery, patients in the experimental group will receive irrigation of 1 ml (40 mg/mL) triamcinolone around the bed of applied scleral buckle distributed equally in all 4 quadrants (.25 ml per quadrant) under the tenon layer of the eye. Patients in the control group will be given irrigation around the applied scleral buckle of 1 ml balanced salt solution instead of triamcinolone. Patients will be masked to the treatment group assignment. The surgeon cannot be masked, as the triamcinolone solution is white and the balanced salt solution is clear. Intraoperative details will be recorded in the EMR about the surgery in both groups, including duration of surgery, time of irrigation, any additional pharmaceuticals or anesthesia applied, procedures performed, and placement of the buckle. Patient will receive a pill-count form at the end of the visit to keep track of rescue analgesic consumption. All patients

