## Using Triamcinolone Acetonide to Reduce Pain after Scleral Buckle Surgery

		be applied during surgery.					
What Patient will do	Review and sign the consent document	Receive pill count form	Keep track of pain medication s taken on pill-count form	Fill out pain and nausea form. Turn in pill-count and receive second pill-count	Keep track of pain medication s taken on pill-count form	Fill out pain and nausea form. Turn in pill-count	Report pain level from 0-10

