### 8.2 *Describe:*

- *Procedures or safeguards intended to reduce the probability and magnitude of risks.*

Patients will be screened twice for IOP (measured by tonometer) post-surgically to check for ocular hypertension. Patients eyes will also be examined at both visits by the primary surgeon via slit-lamp to determine any adverse events as a result of surgery or the intervention. The surgeon is responsible for the medical safety of all patients and may prescribe any medications deemed necessary for control of side effects of surgery or intervention, including nausea and vomiting.

- *Be sure to describe all drugs and devices used in the research, when they will be administered or used, and their purpose.*  
See 7.1

*Methods used to collect data about subjects. Please upload all data collection forms to Protocol Management*

- Pain and Nausea Survey
- Pill-Count
- IOP (tonometry)

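### Analgesic consumption is a raw pill count, so tablets of different class or strength count equally; this matters most at 1-2 weeks

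*Combined protocol and SAP*

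**What the plan says.** Section 4.1 has two analgesic endpoints in the same unit: "Significant reduction in analgesics consumed post-operatively (self-reported pill count) at 1-day post op" and "Significant reduction in analgesics consumed post-operatively (self-reported pill count) at 1-2 weeks post op". Section 5.2 analyses analgesic consumption in the same way as the primary endpoint, by Student's t-test. Neither section says how tablets of different drugs or strengths are combined.

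Under 8.1 the patient leaves surgery with a form to "keep track of rescue analgesic consumption", and the visit table repeats the instruction for both home periods: "Keep track of pain medication s taken on pill-count form". The drug list in 7.2 holds triamcinolone and the local anaesthetic ("Marcaine (Bupivacaine Hydrochloride .75%). FDA Approved"), with no oral analgesic.

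On masking, 8.1 states: "The surgeon cannot be masked, as the triamcinolone solution is white and the balanced salt solution is clear". At the day-1 visit, after the pain form and first pill sheet have been handled, the surgeon looks at the pain and nausea scores and may prescribe any medication judged necessary, with pain named explicitly. Section 8.2 adds a general clause: the surgeon "may prescribe any medications deemed necessary for control of side effects of surgery or intervention, including nausea and vomiting".

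Section 3.3 notes that some physicians use opioids after this operation, says the investigators would like to avoid that, and gives fewer narcotic prescriptions as part of the study's significance.

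**The concern.** A tablet is not a unit of analgesia. Two patients can take the same number of tablets and very different doses, or the same dose in different numbers of tablets. The t-test in 5.2 would then compare something other than consumption.

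Two routes could turn this into a misleading comparison. First, the surgeon knows the allocation and may add drugs at the day-1 visit, so the mix of tablets can come to differ by arm. Second, even with wholly impartial prescribing, a surgeon who has just seen the pain scores may give stronger tablets to patients in more pain. If triamcinolone works, more of those patients will be controls. They may then need fewer tablets for the same relief, which masks a real saving.

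At stake are the two analgesic endpoints, mainly the one at 1-2 weeks, and any statement about narcotics drawn from them.

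**Working it through.** **1. The plan's own figure.** The only sample-size figure is for pain (14.1). Pooled SD = √((1² + 2.5²)/2) = 1.904, so d = 2/1.904 = 1.05, as stated. At two-sided alpha 0.01 and power 0.80, the t-test needs 22.9 per arm. Dividing by the Mann-Whitney efficiency, 22.9/0.955 = 23.98, so 24 per arm and 48 in total. N = 48 reproduces and is untouched by this point. No figure is given for analgesic consumption.

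**2. Which count is exposed.** The order of events in 8.1 is:
- Surgery, then rescue at home on the first supply.
- Day-1 visit: pain form completed, first pill sheet collected, second sheet issued.
- Surgeon's examination, with explicit freedom to prescribe for pain.
- Home period on the second sheet, then the 1-2 week visit.

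The explicit freedom therefore acts on the second count. The day-1 count depends on the initial supply, which the text does not describe, and on the general clause in 8.2, which does not name pain.

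**3. Arithmetic of a mixed count.** Assume that an arm needs a mean dose D, in single-strength tablets, and that a share s of its patients, unrelated to need, has double-strength tablets. Ignoring rounding to whole tablets:

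mean tablets = D(1 − s) + (D/2)s = D(1 − s/2).

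- *Hiding a saving.* With D = 6 in controls and s = 0.5, controls average 6 × 0.75 = 4.5 tablets. A triamcinolone arm on single strength that truly needs 4.5, a quarter less dose, shows no difference. With s = 0.25 the control mean is 6 × 0.875 = 5.25, and a true saving of one eighth is hidden.
- *Creating a saving.* With D = 6 in both arms and s = 0.5 in the triamcinolone arm only, the means are 4.5 and 6: an apparent saving of a quarter with no difference in dose.

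**4. Illustration of significance.** Simulated trials had 24 per arm and the same dose need in both arms (mean 6 single-strength tablets, SD 3 to 5, rounded up to whole tablets), with a two-sided t-test on raw pills. All these inputs except the number per arm are assumptions. The ranges span the two SDs.

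| Share on double strength, one arm / other | Significant at 0.05 | Significant at 0.01 |
|---|---|---|
| 50% / 50% | 4-5% | 0.6-1.0% |
| 25% / 50% | 8-14% | 2.0-4.5% |
| 25% / 75% | 24-47% | 8-24% |

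The arm with more double-strength tablets shows the lower count, whichever arm that is. With an equal mix, false positives stay at or below the nominal level. The harm comes from imbalance between arms, and the documents do not say whether any will occur.

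**The case against.** The strongest reply is that the missing detail may exist elsewhere. The revision history records a pain protocol added at Revision 1, and its content is not in the text reviewed; nor is the pill-count form. Section 1.0 also lists analgesic consumption on the 1-2 week survey beside a separate pill count, so a second source is planned there and may capture the drug. This stands: a reader might infer that the trial has no rescue regimen, and the documents do not support that. Yet a common first order would still leave 4.1 counting tablets and the surgeon free to add others after day 1.

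A reader might also infer that surgeons will order differently by arm before the day-1 score. The surgeons' favourable impression in 3.2 makes this conceivable, but the permission that names pain comes after the day-1 form, the patient is masked, and an order is not intake. For day 1 it is conjecture.

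A third tempting inference is that the trial has a narcotic-sparing hypothesis that the count fails to test. It has none: 2.2 and 4.1 speak of analgesics in general, and 3.3 describes significance. The fair statement is that the count cannot support a claim about narcotics.

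Finally, one might wish to quote a loss of power. The scores in 14.1 are post-operative pain scores, not pain before rescue, and the documents give no rescue figures. Any such number would describe the model used, not this trial.

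**Conclusion.** The point holds for the unit of measurement in 4.1 and its comparison in 5.2. It is firmest at 1-2 weeks, where 8.1 gives an unmasked surgeon open discretion over pain medication during the counting period. At day 1 it depends on an initial supply that the text reviewed does not describe.

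The size cannot be derived from the documents. The working shows only direction: unequal mixes can create or hide a difference, while a mix unrelated to arm or pain does not raise false positives. The point rests on more than one drug or strength being in use, which the plan permits but does not say will happen.

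A reader might infer that the primary result is biased towards triamcinolone. That does not follow. If control patients took more or stronger rescue before the day-1 score, their pain would fall and the difference would shrink, which is conservative. Section 5.2 already compares day-1 pain without adjustment for rescue, so the primary analysis needs no change. The affected endpoints are secondary; the change is worth making because it is cheap and because an unrecorded strength may not be recoverable, since 8.3 has the paper forms discarded after data entry.

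**What to change.** - **Pill-count form:** record drug, strength and number taken, if it does not already.
- **4.1:** replace the raw count with dose, for example: *analgesic dose taken up to day 1 and from day 1 to the 1-2 week visit; opioids in opioid equivalents by a conversion table fixed before data are seen by arm, non-opioids separately in mg of each drug.*
- **5.2:** apply the planned comparison to these doses in place of pills.
- **8.1:** record each analgesic added by the surgeon, with date and reason, and report additions by arm. The surgeon's freedom to treat is unchanged.
- **7.2 or 8.1:** cite the Revision 1 pain protocol as the initial rescue order common to both arms, if it sets one.

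The cost is a form column, a fixed conversion table, a short amendment, and agreement among the operating surgeons on recording additions. Splitting by class gives more than one result per visit. Patients already enrolled may have raw counts only. Unequal additions by the unmasked surgeon would be visible but not prevented.

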### 4.2 *Describe any primary or secondary safety endpoints. These should be included for all studies that are greater than minimal risk.*

- Primary: No significant difference in ocular hypertension 1-2 weeks post-operatively, defined as IOP of >5mmHg above baseline
- Secondary:
  - No significant difference in infections following surgery
  - No significant difference in hypersensitivity following surgery

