## 5.0 Study Design and Statistical Analysis Plan

*5.1 Describe the basic study design/approach*

Simple randomized controlled trial comparing two groups in reducing post-operative pain from scleral buckle surgery -

1. Peribulbar irrigation of triamcinolone acetonide (Experimental Group)
2. Balanced Salt Solution (Control Group)

*5.2 Describe corresponding data analysis plan/approach*

Parametric analysis of experimental and control groups using students' t-test for primary endpoint, secondary endpoint of pain and analgesic consumption will be analyzed similarly. Secondary endpoints of nausea and vomiting score will be analyzed via non-parametric analysis (Mann-Whitney U test)

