## Using Triamcinolone Acetonide to Reduce Pain after Scleral Buckle Surgery

used. Corticosteroids may enhance the establishment of secondary ocular infections due to fungi or viruses. If an infection occurs during corticosteroid therapy, it will be promptly controlled by suitable antimicrobial therapy.

**Elevated Intraocular Pressure:** Increases in intraocular pressure associated with triamcinolone acetonide injection have been observed in 20-60% of patients. This may lead to glaucoma with possible damage to the optic nerve. Effects on intraocular pressure may last up to 6 months following injection and are usually managed by topical glaucoma therapy. A small percentage of patients may require aggressive non-topical treatment. Intraocular pressure as well as perfusion of the optic nerve head will be monitored and managed appropriately. As our study will be irrigating the peribulbar space rather than injecting into the posterior capsule of the eye, we expect our rate of elevated IOP to be much lower than that determined by the FDA.

**Endophthalmitis:** The rate of infectious culture positive endophthalmitis is 0.5%. Proper aseptic techniques will always be used when administering triamcinolone acetonide. In addition, patients will be monitored following the injection to permit early treatment should an infection occur.

**Cataracts:** Use of corticosteroids may produce cataracts, particularly posterior subcapsular cataracts. As our study will be irrigating the subtenon's space rather than injecting into the posterior capsule of the eye, we expect our rate of cataracts to be much lower than that determined by the FDA.

**Patients with Ocular Herpes Simplex:** Corticosteroids should be used cautiously in patients with ocular herpes simplex because of possible corneal perforation. Corticosteroids should not be used in active ocular herpes simplex. We will be excluding all patients with ocular herpes simplex.

Systemic reactions are exceedingly rare in ophthalmic administration of corticosteroids but are included below for completeness:

**Cardiovascular:** Bradycardia, cardiac arrest, cardiac arrhythmias, cardiac enlargement, circulatory collapse, congestive heart failure, fat embolism, hypertrophic cardiomyopathy in premature infants, myocardial rupture following recent myocardial infarction, pulmonary edema, syncope, tachycardia, thromboembolism, thrombophlebitis, vasculitis

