### 21.1 Describe:

- *The plan to periodically evaluate the data collected regarding both harms and benefits to determine whether subjects remain safe (e.g., periodic reporting to the IRB, establishing a data monitoring*

*committee, reporting data monitoring committee findings to the IRB and the sponsor).*

The patient's IOP will be measured at baseline prior to the surgery, as well as 24 hrs post-op and 2 weeks post-op. This is done to monitor ocular hypertension, a potential side-effect of both the surgery and TA treatment. Patients will also have two normally scheduled follow-up visits with the surgeon who will be monitoring for any other adverse events such as hypersensitivity or infection. If adverse events occur that may be related to the intervention, they will be reported to the IRB promptly. The data will also be monitored after every 10th patient completes the protocol for any statistically significant differences in the primary or secondary safety endpoints. If this occurs, it too will be reported to the IRB promptly.

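### Section 4.2 takes a non-significant test as the safety result in a trial sized only for pain; at 24 per arm, a true doubling of ocular hypertension would often meet it

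*Combined protocol and SAP*

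**What the plan says.** Section 4.2 gives the main safety endpoint as "Primary: No significant difference in ocular hypertension 1-2 weeks post-operatively, defined as IOP of >5mmHg above baseline". The two secondary safety endpoints, infections and hypersensitivity, take the same form.

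The rest of the plan does not support a safety test:

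- **Power.** Section 4.1 says "We are powered to detect a reduction in 2 points on the NRS scale". The only sample-size calculation (Section 14.1) is also for pain: alpha .01, power 0.8, effect size 1.05, n = 48.
- **Tests.** Section 5.2 names the t-test for pain and analgesic use, then adds "Secondary endpoints of nausea and vomiting score will be analyzed via non-parametric analysis (Mann-Whitney U test". It names nothing for ocular hypertension, infection or hypersensitivity.
- **Expected rate.** Section 17.1 reports raised pressure in 20-60% of patients after triamcinolone injection. For irrigation it says "we expect our rate of elevated IOP to be much lower than that determined by the FDA", without a figure.
- **Monitoring.** Section 21.1 reviews the data each time a tenth "patient completes the protocol for any statistically significant differences in the primary or secondary safety endpoints", and reports to the IRB if one is found. The point at which a patient has completed the protocol is not defined. Section 1.0 says "Each pt. is enrolled for 2 weeks", while Section 11.1 gives participation as 6 months.

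**The concern.** Failing to find a difference is not the same as showing there is none, and in a small trial the gap between the two is wide. As worded, Section 4.2 counts the safety endpoint as met whenever the test fails to reach significance. The smaller the trial and the rarer the event, the easier that is.

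Ocular hypertension is a risk that Section 17.1 itself attaches to this drug. The protocol expects its rate to be low, and a doubling is hardest to detect at low rates. Section 3.3 hopes that a positive result will help settle a standard of care. A statement of no significant difference in safety could accompany that result while the data remained compatible with twice the rate of raised pressure.

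The looks in Section 21.1 carry the same weakness, because significance is the only stated trigger for reporting a comparison between arms. If completion means the 6-month call, each look would also come more than five months after the 1-2 week pressure data were available.

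**Working it through.** **1. The plan's own figure.** From Section 14.1, the difference is 3 − 1 = 2 and the SDs are 1 and 2.5. Pooled SD = √((1² + 2.5²)/2) = 1.904, so d = 2/1.904 = 1.05. A two-sample t-test at two-sided .01 and power 0.80 needs 23 per arm, 46 in total, and 24 per arm gives power 0.82. The stated 48 is therefore reproduced within 2 as a total for pain.

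**2. Inputs for safety.** About 24 per arm (48 patients, coin-flip allocation, Section 8.1). Assumed, because the documents give neither: control rates of 10%, 20% and 30%, and two-sided alpha .05. Doubling gives experimental rates of 20%, 40% and 60%, which span the 20-60% in Section 17.1.

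**3. Chance that a true doubling meets the endpoint.** For control rate p and experimental rate 2p, sum Bin(x; 24, p) × Bin(y; 24, 2p) over all 25 × 25 outcomes (x, y) for which the test gives p ≥ .05.

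| Control vs experimental | Fisher | Uncorrected chi-square |
|---|---|---|
| 10% vs 20% | 90.3% | 83.3% |
| 20% vs 40% | 76.4% | 66.7% |
| 30% vs 60% | 52.9% | 41.0% |

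Variants:
- Averaged over coin-flip arm sizes, Fisher gives 90%, 74% and 50%.
- At .01, the only alpha in the documents, Fisher gives 98%, 92% and 75%.

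**4. What the trial could detect.** A large excess, 20% vs 60%, has power 76% (Fisher) or 84% (chi-square). For 80% power the experimental rate must reach:

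| Control rate | Fisher | Chi-square |
|---|---|---|
| 10% | 49% | 44% |
| 20% | 62% | 58% |
| 30% | 73% | 69% |

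By the normal approximation, detecting a doubling with 80% power at two-sided .05 needs 199, 82 and 42 per arm at control rates of 10%, 20% and 30%.

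**5. Examples.** With 11/24 events against 5/24, the difference is 6/24 = 25 points. Fisher p = 0.125, chi-square p = 0.066, and the Newcombe 95% CI runs from −2 to +47 points. The endpoint is met under either test. Even 5/24 against 5/24 leaves an interval of −23 to +23 points. For infections, 4/24 against 0/24 gives Fisher p = 0.11.

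**6. The looks.** Exact recursion, each patient allocated by coin flip, looks at 10, 20, 30 and 40 patients. The cumulative chance that at least one look has p < .05:

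| Experimental vs control | Test | By 20 patients | By 40 patients |
|---|---|---|---|
| 40% vs 20% | Fisher | 10% | 27% |
| 40% vs 20% | Chi-square | 19% | 38% |
| 60% vs 20% | Fisher | 33% | 72% |
| 60% vs 20% | Chi-square | 49% | 81% |

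With equal arms of 24, the chance that a doubling is never significant at any look or at the end (Fisher, .05) is about 88%, 71% and 47%.

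**The case against.** The strongest reply is that Section 4.2 only states expected results. Section 4.1 words its endpoints the same way, a small trial sized on efficacy is not a defect in itself, and no passage says a safety claim will follow from non-significance. Nor does the plan leave patients unprotected. Section 8.2 says "Patients will be screened twice for IOP (measured by tonometer) post-surgically to check for ocular hypertension" and adds slit-lamp examination at both visits. Section 21.1 says "If adverse events occur that may be related to the intervention, they will be reported to the IRB promptly", and this does not depend on a significant difference. Both points about patients and sample size stand, and they confine the harm to the safety inference and to reporting by arm. They do not rescue the wording, because an endpoint defined as no significant difference is met by any non-significant test.

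The numbers can also be challenged. The control rates and the doubling are assumed, so the percentages illustrate and do not measure this trial. Fisher is conservative here: its actual type I error is 1.7-2.6% at rates of 10-30%, against 4.7-5.4% for chi-square. Part of the Fisher figures reflects the choice of test, and by chi-square a rise from 30% to 60% is found more often than not. Chi-square is in turn unreliable at the 10-patient look. The looks also raise false alarms: with identical rates of 20-30%, at least one fires by 40 patients with probability 5-6% (Fisher) or 11-13% (chi-square). All of this is fair, and none of it makes non-significance good evidence of safety.

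Finally, Section 21.1 does not say that other comparisons are withheld from the IRB. That is true, but significance is the only trigger it gives for reporting one.

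**Conclusion.** The safety endpoints are wrong as written and should be changed. With 24 per arm and two-sided .05, a true doubling of ocular hypertension would meet the main safety endpoint in 53% to 90% of trials by Fisher, or 41% to 83% by chi-square, across control rates of 30% down to 10%. The control rates, the alpha and the full count of 48 evaluable patients are assumptions. Uneven coin-flip arms and the interim looks shift the Fisher figures by a few points, and the .01 alpha makes them worse. A large excess, such as 20% vs 60%, would usually be seen. The conclusion holds across all these settings: non-significance here does not show comparable safety. The undefined completion point in Section 21.1 is a lesser, linked fault, since it leaves open when the looks occur.

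**What to change.** In Section 4.2, replace the three lines with:

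> Primary: number and proportion of patients with IOP more than 5 mmHg above baseline at 1-2 weeks, by arm, with the risk difference and 95% CI. Secondary: the same for infections and for hypersensitivity. No conclusion of safety will be drawn from a non-significant test.

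In Section 21.1, send event counts by arm to the IRB at every look, whether or not a difference is significant. For these looks, define completion as the 1-2 week visit, when the main safety data exist.

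The cost is wording in two sections, with no new data, visits or patients. Each look needs a short table of counts by arm, prepared by someone other than the blinded examiner. The trial also gives up the option of presenting a non-significant difference as evidence of safety.
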